# AIM 1: Determine the impact of timed rectal evacuation on anorectal dysfunction in MS patients

We will conduct a four week, single-center, randomized, double-blind placebo controlled clinical trial designed to assess the efficacy of timed rectal evacuation in improving the subjective global assessment of bowel symptoms in a cohort of patients with mild-to-moderate severity MS disease. Patients will be randomized 1:1 to administer either placebo or bisacodyl 10 mg rectal suppositories every other day during the 4 week trial. The primary endpoint will be the change in patients' rating of bowel symptom severity (10 point rating scale) at end of 4 weeks compared to baseline values. We will define an adequate treatment response as greater than a 30% reduction in symptom severity using an intention-to-treat analysis.

AIM 2: Determine the predictors of treatment response and impacts on quality of life

We plan to collect information on the patients' assessed severity of baseline and treatment-associated anorectal dysfunction, their impact on quality of life, as well as daily bowel diaries. Patients also will undergo anorectal sensory and manometric testing as a part of their routine clinical care. Enrolled patients that complete the study will be assessed for study medication compliance. All of these measures will be used to explore factors that are associated with treatment response. Changes in assessments of anorectal dysfunction-related quality of life will serve as key secondary end-points.

This proposal will significantly advance MS care and management by developing the evidence to support the adoption of a simple, safe, and cost-effective clinical treatment algorithm for anorectal dysfunction in the MS population. This paradigm for anorectal dysfunction management could be applicable to a majority of MS patients, and the treatment algorithm could be introduced to patients by nurses or mid-level clinical providers during points of routine MS patient care. Importantly, the treatment could be effectively accomplished by most patients and their caregivers at home. The findings of this investigation could also have a broader influence on care models for anorectal dysfunction associated with a range of other neurological illnesses, such as Parkinson's Disease, ALS, or stroke.

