# 1.3 Background: Briefly describe previous findings or observations that provide the background leading to this proposal.

There is growing recognition that the factors driving multiple sclerosis (MS)-related disability extend beyond impairments in mobility to include both psychological and physical symptoms that negatively impact patients' quality of life. Anorectal dysfunction, broadly defined as the presence of chronic constipation and/or fecal incontinence, is a common symptom experienced by MS patients that is often ranked as negatively impactful on quality of life as impaired mobility. About 40% of MS patients suffer from chronic constipation, while ~25% of patients experience frequent episodes of fecal incontinence. Mixed forms of anorectal dysfunction are less common, occurring in at least 10-15% of MS patients, but pose a particular therapeutic challenge. Because of the daily impact of these common symptoms, anorectal dysfunction places a tremendous burden on MS patients and their caregivers.

Normal defecation patterns require precise conscious and unconscious sensorimotor functions to support the perception of rectal filling, to retain stool in the rectum without anal leakage, and to allow for volitional elimination of stool without difficulty. MS patients may be especially prone to developing anorectal dysfunction because even subtle impairments in sensation from the anorectum and/or the timing and efficacy of coordinated abdominal, pelvic floor, and anal muscle contractions are sufficient to generate symptoms. Regardless of subtle differences in the underlying mechanisms that lead to anorectal dysfunction in any one MS patient, an ideal therapeutic approach should be safe, flexible, straightforward, and effective enough to help most patients.

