During Phase 2, patients will meet the PI / Co-PI in the UPMC Digestive Disorders Center (DDC) for anorectal function testing (anorectal sensory and High Resolution Anorectal Manometry (HRAM) testing), which typically takes about 45 minutes. This is a one time, routine test that is performed in patients with anorectal dysfunction. It involves the transanal placement of a thin manometry catheter with inflatable balloon into the rectum. The patients' threshold to first sensation of rectal filling, urgency, and pain, basal anal resting pressure, voluntary anal squeeze pressure, and the rectal-anal inhibitory reflex (RAIR) to rectal distention and during simulated strain, as well as the ability to evacuate a 50 cc volume rectal balloon within one minute are all recorded variables and constitute normal components of such testing. The PI/Co-PI will meet with patients in the DDC GI lab around the time of the anorectal testing, and based on the clinical assessment of dominant bowel symptoms, provide patients with guidance on baseline interventions (either laxative or anti-diarrheal use). For example, the use of oral therapies is predicated on patients' typical stool form (using the Bristol Stool Scale 1-7) - the goal is to achieve a typical bowel movement of a 3-5 in consistency. Patients with Bristol 1-2 stools (hard) will use 8.5 - 42 grams of PEG-3350 laxative per day, while those with Bristol 6-7 (loose) will use 0.5 - 4 grams of loperamide per day, titrated to the goal. At the end of Phase 2 visit, patients will be given instructions on study medication use and will obtain the study drug (double-blinded; study drug "blister" packets would have been previously randomized by the pharmacy and delivered to the DDC). Patients will be encouraged to continue daily bowel diaries for the ensuing 4 weeks of the study trial period. Phase 2, including the physiological testing assessment and meeting with the PI/Co-PI, should take about 1.5 hours in total.

During the next 4 weeks, patients will use recommended oral therapies in addition to the every other day use of the rectal suppository study medication. They will record events in their daily bowel diary.

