Finally in Phase 3, after the 4 week study period, patients will meet with the study coordinator to collect unused study medication and completed bowel diaries, and then undergo final reassessments of bowel dysfunction severity and QOL measures. This process could take up to 1 hour. After the questionnaires are completed, patients and the PI/Co-PI will be debriefed (i.e. study arm allocation will be revealed) before having a routine followup clinic visit (continuity of care).

- 1) The study coordinator will identify and screen potential study subjects (by accessing the "UPMC Multiple Sclerosis and Related Disorders Registry" (PRO12010609) to identify prospective subjects), coordinate the informed consent process with the PI/Co-PI, collect intake questionnaires, and provide instruction on bowel diaries (Phase 1). The coordinator will schedule referrals for anorectal function testing and follow-up DDC visit, and contact patients during the 4-week trial period to verify compliance. Finally, the coordinator will collect bowel diaries and remaining medications at study end, administer study exit questionnaires, and then debrief subjects and the PI/Co-PI once the blind is broken (Phase 3).
- 2) DDC GI nursing staff routinely performs HRAM studies and will do so in this study. The PI/Co-PI will be involved in clinical care and recommendations both during Phase 2 and Phase 3 (and beyond).
- 3) MS Physicians will be involved in initial identification of potential subjects and all MS-related continuity of care.
- 4) Falk Pharmacy serves UPMC for clinical trials, and staff will ensure the 1:1 randomization and distribution of either twenty placebo or biscodyl 10 mg rectal suppositories (used every other day over 4 weeks during the study period). Falk Pharmacy staff is experienced in running clinical trials and maintaining double-blind study conditions between subjects and investigators. Patients will receive a slight excess number of suppositories in order to assess study medication compliance at trial end.

STUDY MEASURES: We plan to obtain the following information from all enrolled patients:
1) Primary Patient-Reported Outcome Measure: "Using a scale of 1 to 10 (1 being no problem and 10 being maximally impactful symptoms), how would you rate the severity of your bowel symptoms over the past 2 weeks?"

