3.8 Does this research study involve neonates of uncertain viability or nonviable neonates?

\* No

[reviewer notes¬]

- 3.9 Fetal Tissues: Does this research involve the use of fetal tissues or organs?
  - \* No

[reviewer notes¬]
--->

3.10 What is the total number of subjects to be studied at this site, including subjects to be screened for eligibility?

Note: The number below is calculated by summing the data entered in question 3.11. Any additions or changes to the values entered in 3.11 will be reflected in 3.10.

- \* 400
- 3.11 Identify each of the disease or condition specific subgroups (include healthy volunteers, if applicable) that will be studied.

Click on the "Add" button and specify for each subgroup:

- 1) how many subjects will undergo research related procedures at this site; and
- 2) if applicable, how many subjects will be required to undergo screening procedures (e.g., blood work, EKG, x-rays, etc.) to establish eligibility. Do Not include subjects who will undergo preliminary telephone screening.

\*

Subgroup	Number to undergo research procedures	Number to undergo screening procedures
View MS patients	70	400

- 3.12 Provide a statistical justification for the total number of subjects to be enrolled into this research study at the multicenter sites or this site.
  - \* Described below:

The primary outcome measure is the group mean difference in subjective severity ratings of bowel symptoms using a 10 point scale. It is generally regarded that a 3-point reduction represents a clinically meaningful change using such a scale, and similar

Section: Section 3 - Human Subjects

research studies using patient-reported outcomes have reported standard deviations ranging around ~2.5 points on a 10 point scale. However, we do not have baseline data in this population to estimate variance, and thus we took a conservative estimate with an expected standard deviation of 4 points. Given these assumptions, we will need 28 patients in each study arm to detect at least a 3 point reduction in symptom severity, with a power of 0.80, alpha=P<0.05 in a two-tailed analysis.

Thus, the study is adequately powered if enrollment reaches 56 patients. However, to ensure adequate numbers in an intention-to-treat analysis, we will plan for a ~20% patient drop-out rate. Therefore, we will aim to enroll 70 patients in total.

[reviewer notes¬]

3.13 Inclusion Criteria: List the specific criteria for inclusion of potential subjects.

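### Constipation and incontinence patients are pooled with no stated stratification and no adjustment for bowel type; incontinence at baseline should be a pre-specified factor in the primary analysis.

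*Combined protocol and SAP*

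**What the plan says.** Section 3.13 admits patients with chronic constipation and/or fecal incontinence. Section 1.3 gives the background frequencies: "About 40% of MS patients suffer from chronic constipation, while ~25% of patients experience frequent episodes of fecal incontinence". It adds that mixed forms occur in at least 10-15% and are especially hard to treat.

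Allocation is described in three places:

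- Aim 1 (section 1.2): "Patients will be randomized 1:1 to administer either placebo or bisacodyl 10 mg rectal suppositories every other day".
- Section 2.6, Phase 2: the study drug "packets would have been previously randomized by the pharmacy and delivered to the DDC".
- Section 2.6, item 4: pharmacy "staff will ensure the 1:1 randomization and distribution of either twenty placebo or biscodyl 10 mg rectal suppositories".

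None of these names a stratification factor, a block size, minimisation or a method of generating the sequence.

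Section 2.18 compares arms by Fisher's exact test for categorical data and Student's t-test for continuous data. Logistic regression appears only as a way to find predictors of response. The primary outcome is given as a mean change in some places (Aim 1, section 3.12) and as a reduction of more than 30% in others (sections 2.6 and 2.17). Neither form is adjusted for bowel type.

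**The concern.** The protocol itself treats bowel type as relevant. Constipation and incontinence each have their own severity and quality-of-life instruments, and the abstract promises to predict which patients benefit. Whether a patient has incontinence is known before a packet is issued: severity questionnaires are completed at Phase 1, a baseline diary recording incontinence episodes follows, and packets are handed out at the end of the Phase 2 visit. Yet no stated step uses this information, in allocation or in the comparison of arms.

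If the two types of patient respond differently, a chance difference in their mix moves the observed treatment effect in a 70-patient trial, and the planned tests do not remove that movement. At stake are precision and how clearly one result can be read. The validity of the randomised comparison is not at stake.

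**Working it through.** **1. The plan's own sample size.** Section 3.12 states "we will need 28 patients in each study arm to detect at least a 3 point reduction in symptom severity", with an "expected standard deviation of 4 points" and "with a power of 0.80, alpha=P<0.05 in a two-tailed analysis".

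n per arm = 2 × (1.96 + 0.84)² × 4² / 3² = 27.9, so 28. Two arms give 56, and 56 / 0.80 = 70, matching "we will aim to enroll 70 patients in total". The figure reproduces and is not disputed. Equal arms are 35 each.

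**2. Share with incontinence among enrolled patients.** This is not stated. From section 1.3:

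- mixed form counted inside both figures: 25/(40 + 25 − 10) = 25/55 = 45% to 25/(40 + 25 − 15) = 25/50 = 50%
- mixed form counted separately: (25 + 10)/(65 + 10) = 35/75 = 47% to (25 + 15)/(65 + 15) = 40/80 = 50%
- mixed form ignored: 25/65 = 38.5%

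These are population frequencies, so shares of 20% and 25% are added as a sensitivity range.

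**3. Chance of a gap of 15 points or more, unstratified arms of 35.** Normal approximation: SE = √(2p(1 − p)/35) and chance = 2 × [1 − Φ(0.15/SE)]. At p = 0.50, SE = 0.1195 and 0.15/SE = 1.255, giving 20.9%. The exact column uses two independent binomials. There a gap of 15 points means at least 6 patients (17.1 points), because 5 patients is 14.3 points.

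| Share with incontinence | Normal | Exact |
|---|---|---|
| 20% | 11.7% | 9.9% |
| 25% | 14.7% | 12.8% |
| 38.5% | 19.7% | 17.6% |
| 45.5% | 20.8% | 18.6% |
| 50% | 20.9% | 18.8% |

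Fixing the total number of incontinent patients (26 to 36 of 70) gives 14 to 15% when that total is odd and 22 to 23% when it is even. This is the same range with coarser steps.

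**4. What such a gap does to the estimate.** The differences between bowel types below are assumptions; the documents give none.

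- *Responder endpoint.* Assume 30% response with incontinence and 55% without, and a 48% share. Overall response = 0.48 × 0.30 + 0.52 × 0.55 = 43%. SE of the arm difference = √(2 × 0.43 × 0.57/35) = 11.8 points. A 15-point gap shifts the difference by 0.15 × 25 = 3.75 points (0.32 SE). A 20-point gap shifts it by 5 points (0.42 SE).
- *Mean change.* Assume the types differ by 2 points. A 15-point gap shifts the difference by 0.3 points, against an SE of 4 × √(2/35) = 0.96 (0.31 SE).

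**5. What adjustment can recover.** Under the same assumptions, incontinence explains 0.48 × 0.52 × 0.25² / (0.43 × 0.57) = 6% of the variance of the responder endpoint. For mean change it explains 0.48 × 0.52 × 2² / 4² = 6%. The gain is real but modest.

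**The case against.** The case against rests on four arguments.

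**The method is undescribed, which is different from being simple.** A reader might infer a single unstratified list. The documents do not say so; an experienced trial pharmacy preparing packets in advance may well use blocks. This stands, so the figures above are conditional on no stratification. It also removes a related inference, that a plain list endangers the 28-per-arm target. Under coin-flip allocation there is a 12% chance that the smaller arm has 28 or fewer, but no section states coin-flip allocation. Even at 28 against 42, 20% drop-out leaves 22.4 and 33.6, and power falls only from 80.1% to 78.5%. Blocking for arm size would not, however, balance bowel type: the exact column above already assumes 35 per arm.

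**Chance imbalance is already covered by the test's error rate.** This stands. The unadjusted tests remain valid.

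**Incontinence may not be the factor that matters.** A reader might call it the strongest clinical divider, or suppose that it decides the oral agent. No section ranks it as a predictor. Section 2.6 ties oral therapy to stool form on the Bristol scale, so an incontinent patient with hard stools would fall in the laxative group. Section 1.3 in fact seeks one approach to help most patients regardless of mechanism. Differential response is plausible but not shown.

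**The background frequencies do not describe the enrolled sample.** The 25% refers to frequent episodes among all MS patients, while enrolment is by registry and referral with a disability limit. This stands, and is why the lower shares are in the table.

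What remains is that a baseline factor the trial records, and regards as relevant to response, has no place in the primary comparison.

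**Conclusion.** The point holds as one of precision and interpretability. If allocation is unstratified, the chance of a 15-point or larger gap in the incontinence share is about 10 to 21% for enrolled shares of 20 to 50%, and about 18 to 21% at the shares suggested by section 1.3. The resulting shift is about 0.3 SE for a 15-point gap and 0.4 SE for a 20-point gap, resting on assumed response differences between bowel types.

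A reader might infer that the treatment comparison is biased or its type I error inflated. It is neither. The planned search for predictors is not defeated either, since logistic regression does not need balanced cells. The change is worth making because it is nearly free, not because the trial would fail without it.

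**What to change.** **Analysis (section 2.18).** Pre-specify incontinence present or absent at baseline as an adjustment factor in the primary analysis. Use a stratified test or logistic regression for the responder endpoint, naming one in advance, and ANCOVA for the mean change. Define the factor from the Phase 1 FISI and the baseline diary, and fix the threshold for presence before any allocation is revealed. The planned Fisher and t-tests can stay as sensitivity analyses. The cost is one extra model term, with little gain if bowel type turns out not to be prognostic.

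**Allocation (section 2.6).** State how the sequence is generated and whether blocks or strata are used. Stratifying the packets by the same factor is optional. Blocks of 4 would cap the gap at 2 incontinent patients (2/35 = 5.7 points) and blocks of 6 at 3 patients (8.6 points). Blocks as small as 2 and 4 should nevertheless be avoided. Sections 2.6 (Phase 3) and 4.14 reveal each patient's arm to the PI/Co-PI at that patient's exit, and sections 4.12 and 2.6 have the same people obtain consent and guide oral therapy for later patients. In a block of 2, one revealed allocation determines the other. If packets are stratified, use larger blocks of varying, concealed size, or withhold allocations from staff who consent and manage later patients. The cost is a second packet sequence and some spare packets; withholding allocations would also mean changing the debriefing arrangement.

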- 2) Daily Bowel Diaries patients will record the consistency (Bristol Stool Scale, 1-7), number of bowel movements (BM), and occurrence of any fecal incontinence (FI) episodes each day. This data will be used to abstract BM and FI weekly frequency, as well as the mean change in stool consistency during the study period.
- 3) Patient Assessment of Constipation Symptom Questionnaire (PAC-SYM)
- 4) Fecal Incontinence Severity Index (FISI)
- 5) Patient Assessment of Constipation QOL (PAC-QOL)
- 6) Rockwood Fecal Incontinence Quality of Life Scale (FIQL)
- 7) SF-36 health status questionnaire
- 8) Study Medication Compliance
- 9) Anorectal Sensory and High Resolution Anorectal Manometry Testing: First sensation of rectal filling, urgency, and pain, basal anal resting pressure, voluntary anal squeeze pressure, and the rectal-anal inhibitory reflex (RAIR) to rectal distention and simulated strain, as well as the ability to evacuate a 50 cc volume rectal balloon within one minute.

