### **Study Flow Chart:**

Name	Modified Date
STUDY DIAGRAM - UPDATED 10-26-15.pdf	10/26/2015 11:13 AM

[reviewer notes¬]

2.7 Will follow-up procedures be performed specifically for research purposes? Follow-up procedures may include phone calls, interviews, biomedical tests or other monitoring procedures.

\* No

[reviewer notes¬]

2.8 Does this research study involve the use of any questionnaires, interview or survey instruments?

\* Yes

Upload a copy of all materials except for the SCID or KSADS which are on file at the IRB. The use of all instruments must be addressed in question 2.6 and/or question 2.7 (except for an exempt submission where they should be addressed on the appropriate uploaded exempt form).

Name	Modified Date
Primary Endpoint - PAC-SYM and FISI Questionnaires.pdf	11/3/2015 3:24 PM
SF-36 QUESTIONNAIRE in PDF.pdf	11/3/2015 3:24 PM
FIQL .pdf	11/3/2015 3:24 PM
PAC-QOL.pdf	11/3/2015 3:23 PM
Bowel Diary Pages.pdf	11/3/2015 3:35 PM

Previously the name and publisher for commercially available materials were listed in the textbox below but effective 9/1/2015, all materials (except for the SCID and KSADS) must be uploaded using the Add button above.

Each of these questionnaires (PAC-SYM, FISI, PAC-QOL, FIQL, SF-36) are open access.

[reviewer notes¬]

2.9 If subjects are also patients, will any clinical procedures that are being used for their conventional medical care also be used for research purposes?

\* yes

If **Yes,** describe the clinical procedures (and, if applicable, their frequency) that will be used for research purposes:

Anorectal function testing (anorectal sensory function and high resolution anorectal manometry [HRAM]) is commonly used for to help patients with anorectal dysfunction. The testing is typically performed once.

**2.10** The blood sample question was moved to 2.6.1.

[reviewer notes¬]

- 2.11 What is the total duration of the subject's participation in this research study across all visits, including follow-up surveillance?
  - Up to 8 weeks

[reviewer notes¬]

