# 4.14 Will you inform research subjects about the outcome of this research study following its completion?

\* Yes

If **Yes**, describe the process to inform subjects of the results:

Patients and the PI/Co-PI will be debriefed after Phase 3 by the study coordinator. They will then be seen by the PI/Co-PI in a standard follow up clinic visit. The debriefing is a necessary part of the patient's continuity of care, as it may direct changes in patient management (i.e. if a patient did not have a clinical improvement in the placebo arm, they may be offered study medication or its equivalent). As a patient reported outcome is the primary outcome measure, the "results" of the study should be self-evident to patients.

Section: Section 5 - Potential Risks and Benefits

[reviewer notes-]

5.1 Describe potential risks (physical, psychological, social, legal, economic or other) associated with screening procedures, research interventions/interactions, and follow-up/monitoring procedures performed specifically for this study:

\*

	Research Activity:	Bowel Diary
	Common Risks:	No Value Entered
View	Infrequent Risks:	All efforts will be made to keep the information secure. However, there is a small chance of a breach in confidentiality with any medical record keeping.
	Other Risks:	No Value Entered
	Research Activity:	Medical Record Review
	Common Risks:	No Value Entered
View	Infrequent Risks:	There is a small chance of a breach in confidentiality with any medical record review, either by Care Team staff as a part of routine care, or by the study coordinator in the process of

		accessing information from the "UPMC Multiple Sclerosis and Related Disorders Registry" (PRO12010609).
	Other Risks:	No Value Entered
	Research Activity:	Research Intervention
View	Common Risks:	The study medication, bisacodyl 10 mg rectal suppository, is available over-the-counter for routine use for constipation. Side effects of bisacodyl rectal suppositories include stomach discomfort, nausea, faintness, rectal burning, mild cramps, and diarrhea but these are potential issues are uncommon. There are no side effects to taking placebo, but patients could have a risk of continued bowel dysfunction if they do not receive the study drug.
	Infrequent Risks:	No Value Entered
	Other Risks:	No Value Entered
	Research Activity:	Screening and Enrollment

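### No side-effect variable and no record of on-study oral-agent use is planned, so tolerability by arm cannot be reported and the word safe in 1.2 has no planned data behind it

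*Combined protocol and SAP*

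**What the plan says.** All references are to the combined protocol and SAP.

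- **Measures (2.6, Study Measures).** Nine items are to be obtained from every enrolled patient: the 1 to 10 severity rating, the diary, PAC-SYM, FISI, PAC-QOL, FIQL, SF-36, study medication compliance, and anorectal testing. In the diary, "patients will record the consistency (Bristol Stool Scale, 1-7), number of bowel movements (BM), and occurrence of any fecal incontinence (FI) episodes each day". Elsewhere 2.6 puts it more loosely: "They will record events in their daily bowel diary". The form itself (2.8, "Bowel Diary Pages.pdf") is not reproduced.
- **End points and analysis (2.17, 2.18).** The severity rating is the primary end point and the other eight items are listed as secondary. 2.18 contains no safety or tolerability analysis.
- **Expected effects (5.1, Research Intervention).** The protocol lists "stomach discomfort, nausea, faintness, rectal burning, mild cramps, and diarrhea but these are potential issues are uncommon". It gives no rates.
- **Oral agents (2.6, Phase 2).** Patients with hard or loose stools receive PEG-3350 or loperamide, adjusted towards a target stool form. The guidance and the study drug are both given around the Phase 2 visit, and both are used during the following 4 weeks.
- **Contacts.** The coordinator is to "contact patients during the 4-week trial period to verify compliance" (2.6), and 5.1.1 has the coordinator contact patients to check that they are having no problems. Section 2.7 answers No to research follow-up procedures, and its prompt reads "Follow-up procedures may include phone calls, interviews, biomedical tests or other monitoring procedures".
- **Monitoring (5.13).** The monitoring group judges whether the balance of risk and benefit has changed, and reviews ad hoc those serious adverse events that are directly related to study medication.
- **Deliverable (1.2, closing paragraph).** The trial is said to contribute by "developing the evidence to support the adoption of a simple, safe, and cost-effective clinical treatment algorithm".

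**The concern.** A trial that says it will supply evidence for a safe regimen needs at least a planned count of the side effects it expects, by arm, with a denominator. None is described. The monitoring group would be judging risk against benefit from a dataset with no risk variable in it, and the statement in 5.1 that the effects are uncommon could not be tested in this population.

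The second gap concerns co-intervention. Bisacodyl may itself change stool form, and the oral agent is adjusted according to stool form. Oral-agent use could therefore drift apart between arms after randomization. If it is not recorded, a reader of the results cannot tell whether it did, and a difference (or lack of one) in stool form or diarrhea is harder to interpret.

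**Working it through.** **1. Coverage of the effects named in 5.1**

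| Effect | Described item that would capture it |
|---|---|
| Diarrhea | Inferable from daily Bristol score and bowel-movement count |
| Stomach discomfort | None described |
| Nausea | None described |
| Faintness | None described |
| Rectal burning | None described |
| Mild cramps | None described |

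One of six is covered indirectly and five are not described. Because the diary pages and PAC-SYM are not reproduced, this is a statement about the text of 2.6 and 2.17, not about the forms. Symptom items on a questionnaire given at baseline and at Phase 3 would in any case not be an adverse-event record over the 4 weeks.

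**2. Study drug and oral agents**

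- Suppositories: every other day over 28 days is 14 doses. Twenty are supplied, so 20 − 14 = 6 would be returned under full compliance. The count gives total use, not dates.
- Oral agents: no item in 2.6 or 2.17 records product, amount or days. Section 2.14 takes current medication use from the medical record, as MS-related information. That is not on-study use.

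**3. The plan's sample size, which fixes what tolerability data could show**

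3.12 gives a difference of 3, SD 4, two-sided alpha 0.05 and power 0.80. By the normal approximation:

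n per arm = 2 × (1.960 + 0.842)² × (4/3)² = 27.9, so 28; 2 × 28 = 56; 56 / (1 − 0.20) = 70.

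The stated figures reproduce. That is 35 per arm enrolled, and 28 per arm if 20% are lost.

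**4. What recorded side effects would deliver**

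The documents give no rates, so those below are assumptions.

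- Zero events, one-sided 95% upper bound, 1 − 0.05^(1/n): 8.2% for n = 35 and 10.1% for n = 28.
- Chance of seeing an effect at least once in an arm, 1 − (1 − p)^n:

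| Assumed rate p | n = 35 | n = 28 |
|---|---|---|
| 1% | 30% | 25% |
| 5% | 83% | 76% |
| 10% | 97% | 95% |

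- Power for a between-arm difference, Φ[(\|p1 − p2\| − 1.96·se0)/se1], with pooled se0 and unpooled se1. For 5% vs 15% at 35 per arm: se0 = √(0.10 × 0.90 × 2/35) = 0.0717; se1 = √((0.0475 + 0.1275)/35) = 0.0707; Φ[(0.10 − 0.1405)/0.0707] = 28%.

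| Assumed rates | 35 per arm | 28 per arm |
|---|---|---|
| 5% vs 15% | 28% | 24% |
| 5% vs 20% | 47% | 39% |
| 5% vs 30% | 80% | 70% |

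Fisher's exact test, which 2.18 names, is more conservative, so these powers are if anything optimistic. Recording supports description with intervals, not a conclusion that the regimen is safe.

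**The case against.** The case for leaving the plan alone has several parts.

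- **The forms are not visible.** The diary may hold more fields than 2.6 describes, and PAC-SYM may touch on some of the symptoms. This stands: a reader might infer that the diary has no such fields, and the documents do not establish that. What they do establish is that no side-effect variable appears among the listed measures, end points or analyses.
- **Staff do ask about problems.** A reader might infer that side effects would surface only if patients volunteer them. Section 5.1.1 contradicts that, because the coordinator makes the enquiry. What is missing is a described symptom list, a record and a tabulation.
- **Suppository use is measured.** Compliance is a listed measure and a secondary end point, assessed by returned stock with coordinator contact. Only dates of use are missing, and this bears on adherence more than on safety.
- **Randomization protects the comparison.** A reader might infer that benefit or diarrhea could not be attributed to the suppository because oral-agent use is unrecorded. That does not follow. In a 1:1 blinded placebo comparison, a change in oral-agent use caused by the suppository is a consequence of assignment. The intention-to-treat difference still estimates the effect of adding the suppository to adjusted background care, which is the objective in 1.1. The missing data limit explanation only.
- **2.7 may concern post-trial follow-up only.** That is a fair reading, since the in-trial contact is already described in 2.6. It is a point to clarify, not proof that the documents disagree about contact.
- **Safety is not a formal aim, and the numbers are small.** Both are true. The aims concern efficacy, predictors and quality of life, and even good recording could not show safety. But 1.2 makes the claim and 5.13 asks for a risk judgement, so a descriptive record is the least that would match them.

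**Conclusion.** The point holds in a limited form. As described in 2.6, 2.17 and 2.18, the plan collects and analyses no side-effect variable: five of the six effects named in 5.1 have no described item, and diarrhea is available only by inference. The enquiry in 5.1.1 and the ad hoc review of related serious events in 5.13 have no described recording that would yield rates by arm. On-study oral-agent use is not a listed measure. The trial therefore could not report tolerability by arm or show whether oral-agent use differed, and the claim of a safe algorithm would have no planned data behind it.

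The primary analysis is unaffected. The conclusion assumes that the uploaded forms contain no more than the text describes; if they do hold such fields, the remaining gap is their absence from 2.17 and 2.18. It would be wrong to read the point as saying that adding the fields would establish safety: with 35 per arm, zero events is still compatible with a true rate of about 8%. This is a change the sponsor should make, because it is cheap and a stated deliverable depends on it.

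**What to change.** 1. **Diary.** Add daily tick boxes for the effects in 5.1; suppository used, yes or no (for dates, as total use is already counted); and oral agent and amount taken that day.
2. **Contacts.** Have the coordinator ask and record the same symptom list at the contact already planned and at Phase 3, before allocation is revealed.
3. **2.17 and 2.18.** Add side effects by arm and oral-agent use by arm as descriptive summaries, with exact confidence intervals for the proportions, and state that they describe tolerability only.
4. **2.7.** Clarify the No against the contacts in 2.6 and 5.1.1.
5. **Alternative.** If none of this is adopted, remove the word safe from the deliverable in 1.2.

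The cost is a revised diary page, a short contact script and slightly more diary burden. Sample size, visits and staffing do not change.
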